7.2 Venipuncture

The protocol requires patients to have blood drawn for research purposes. The risks of drawing blood are uncommon and may include bleeding, minor infection, and bruising. Commonly, having blood drawn is painful, and rarely can lead to infection at the site of the blood draw. The amount of blood drawn is small and represents an exceedingly small percentage of the amount of the total blood volume and will not represent a significant risk to the patient.

7.3 Carnitine

Given its safety and role in energy production, carnitine has been studied extensively and is widely available. In long-term administration of oral Lcarnitine, mild gastrointestinal side effects have been reported; these include transient nausea and vomiting, abdominal cramps, and diarrhea. Notable, are some reported cases of a "fishy" body odor while taking carnitine supplements. Mild myasthenia is reported in uremic patients; however, this patient population has been excluded from enrolling in our study. In rare cases, patients with or without pre-existing seizure activity have reported seizures to occur, in addition to increase in frequency and/or severity of seizures.

8 Quality Control

Design strategies and monitoring activities throughout the study will ensure the integrity and high quality of the data. Design strategies include training and certification of personnel. The rigorous monitoring program includes data queries and performance monitoring over the time of the trial.

8.1 Personnel training

Prior to enrolling the first subject in the study protocol, study coordinators and research assistance who will perform the outcome assessments will have completed appropriate training. The purpose of training is to ensure that study personnel are carrying out the protocol in a consistent way and are adhering to a good clinical practice guidelines. Staff will have current Human Subjects Training Certification on file.

8.2 Data Quality

The PI and study coordinator will constitute the first line of monitoring of the safety of the human participants. They will perform continuous monitoring of data quality and completion of CRFs. Surveillance for AEs will consist of questioning subjects about potential AEs at every study contact, having subjects report any adverse event to the study team, and having subjects undergo vital sign checks and physical exams during each study visit.

Project team members at Vanderbilt listed as Key Study Personnel with existing electronic health record (HER) system access rights will make use of REDCap Clinical Data Pull (CDP) tools. These tools are designed to enable transfer of relevant study-related data from the Vanderbilt Research Derivative and/or directly from the HER into REDCap.

8.3 Independent Safety Officer

[name] will serve as an independent safety officer and will monitor the trial. The aims of the officer are to safeguard the interests of the trial's participants, potential participants, and investigators, to ensure the safety of the trial's interventions, to monitor the trial's overall conduct, and protect the trial's validity and credibility. [name] serves as an attending physician in the Vanderbilt Medical Intensive Care Unit, the inpatient consult service, and the pulmonary hypertension service. [name] has outpatient clinics where she sees a variety of general pulmonary diseases and pulmonary vascular disease. She will be invited to attend weekly meetings with the PI and study personnel. She will be available to discuss adverse events with the PI and respond to safety concerns from subjects or study personnel.

9 Participant Safety and Confidentiality

9.1 Consent

Written consent will be obtained for enrollment for participants. For each consent process, study personnel will discuss the details of the study, the risks and benefits, and the subject's rights and responsibilities if they choose to participate in the trial and their right to refuse to participate. It will be made clear that their clinical care will not be affected by their decision. Subjects will be permitted to provide verbal consent over the phone prior to being scheduled for a screening visit. A consent script will be provided, and documentation of verbal consent will be noted. Written or e-consent will be obtained at the Visit 1 visit or before.

- 9.2 Safety and Adverse Event
 - 9.2.1 Definitions of Adverse Events
 - **9.2.1.1** Unanticipated Problem (UP): any incident, experience, or outcome that meets all of the following criteria:

1) unexpected (in terms of nature, severity, or frequency) given a) the research procedures that are described in the protocol-related documents, such as the IRB-approved research protocol and informed consent document; and b) the characteristics the subject population being studied;

2) related or possibly related to participation in the research (Possibly related to participation in the research means there is a reasonable possibility that the AE, experience, or outcome may have been caused by the procedures involved in the research); and

3) suggests that the research places subjects or others at a greater risk of harms (including physical, psychological, economic, or social harm) that was previously known or recognized.

- **9.2.1.2** Adverse Event (AE): Any symptom, sign, illness, or experience that develops or worsens in severity during the course of the study. Intercurrent illnesses or injuries should be regarded as AEs. Abnormal results of diagnostic procedures are considered to be AEs if the abnormality:
 - Results in study withdrawal
 - Is associated with a serious AE
 - Is associated with clinical signs or symptoms
 - Leads to additional treatment or to further diagnostic tests
 - Is considered by the investigator to be of clinical significance

- **9.2.1.3** Serious Adverse Event (SAE): Adverse reactions are classified as serious or non-serious. A serious adverse event is any AE that is:
 - Fatal
 - Life-threatening
 - Requires or prolongs hospital stay
 - Results in persistent or significant disability or incapacity
 - A congenital anomaly or birth defect
 - An important medical event

Important medical events are those that may not be immediately life threatening but are clearly of major clinical significance. They may jeopardize the subject and may require intervention to prevent one of the other serious outcomes noted above. For example, drug overdose or abuse, a seizure that did not result in in-subject hospitalization or intensive treatment of bronchospasm in an emergency department would typically be considered serious. All AEs that do not meet any of the criteria for serious should be regarded as **non-serious AEs**.

9.2.1.4 Suspected Adverse Reaction: any adverse event for which there is a reasonable possibility that the drug caused the adverse event. For reporting purposes, "reasonable possibility" means there is evidence to suggest a causal relationship between the drug/investigational product and the adverse event.

9.2.2 Classifying AEs

9.2.2.1 Severity: the intensity of the AE is classified according to the CTCAEv4.0. Grade refers to the severity (intensity) of the AE: If the intensity of an AE worsens during study drug administration, only the worst intensity should be reported on the AE page. If the AE lessens in intensity, no change in the severity is required.

CTCAEv4 Grade 1: mild; asymptomatic or mild symptoms; clinical or diagnostic observations only; intervention is not indicated.

CTCAEv4 Grade 2: moderate; minimal, local, or noninvasive intervention is indicated; limiting to age-appropriate instrumental activities or daily living (ADL; instrumental ADL refers to preparing meals, shopping for groceries or clothes, using the telephone, managing money, etc).

CTCAEv4 Grade 3: severe or medically significant but not immediately life threatening; hospitalization or prolongation of hospitalization is indicated; disabling; limiting to self-care ADL (self-care ADL refers to

bathing, dressing and undressing, feeding self, using the toilet, taking medications, and not bedridden)

CTCAEv4 Grade 4: life-threatening consequences; urgent intervention is indicated.

CTCAEv4 Grade 5: death due to an AE.

In this grading system, severity is not equivalent to seriousness. For example, a SAE would be any events which is life-threatening or disabling (Grade 4) or fatal (Grade 5) or was moderate-severe (Grade 2-3) and required or prolonged hospitalization.

9.2.2.2 Expectedness: AEs must be assessed as to whether they were expected to occur or were unexpected, meaning not anticipated based on current knowledge found in the protocol, investigator brochure, product insert, or label.

Expected: an AE known to be associated with the intervention or condition under study. OHRP defines an unexpected AE as any AE occurring in one or more subjects participating in a research protocol, the nature, severity, or frequency of which is not consistent with either:

1) the known or foreseeable risk of AEs associated with the procedures involved in the research that are described in a) the protocol-related documents, such as the IRB-approved research protocol, any applicable investigator brochure, and the current IRB-approved informed consent document, and b) other relevant sources of information, such as product labeling and package inserts; or

2) the expected natural progression of any underlying disease, disorder, or condition of the subject(s) experiencing the AE and the subject's predisposing risk factor profile for the AE.

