4.2 Study Visits and Contacts

This study will consist of four visits: Visit 1 (0 week), Visit 2 (Week 12), Visit 3 (Week 12+1 day) and Visit 4 (Week 14). The Visit 1 and Visit 3 are both estimated to take approximately 2 hours each. Visit 2 and Visit 4 are both estimated to take approximately 4 hours each. Patients will be consented by the PI, a clinical research coordinator, or a research nurse. Patient's written consent and study procedures will take place at the Pulmonary Vascular Disease Clinic (CPVD), the Clinical Research Center (CRC), there will be no changes to a patient's medication regimen.

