9.2.2.3 Relatedness

1) Definite: the AE is clearly related to the research procedures

2) Probably: the AE is likely related to the research procedures

3) Possible: the AE may be related to the research procedures

- 4) Unlikely: the AE is doubtfully related to the research procedures
- 5) Unrelated: the AE is clearly not related to the research procedures

Possibly related to participation in the research: There is a reasonable possibility that the adverse event experience, or outcome may have been caused by the procedures involved in the research.

For each identified AE, an AE entry on the appropriate form will be completed using the above classifications as soon as possible, updating as necessary. Reporting procedures should be started immediately (within 24 hours) upon learning of a SAE or UP.

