9.2.3 Interpretation of Definitions

9.2.3.1 AE and UP Reporting Period

The study period during which AEs must be reported is normally defined as the period from the initiation of any study procedures to the end of the study treatment follow-up. For this study, the study treatment follow-up is defined as 14 days following the last administration of study treatment.

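### Carnitine tolerability mixes lead-in and on-supplement adverse events: an AE open at first dose keeps only its worst grade, and the count has no on-supplement window

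*Combined protocol and SAP*

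**What the plan says.** All references are to the combined protocol and SAP.

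- **Definition (9.2.1.2).** An AE is "Any symptom, sign, illness, or experience that develops or worsens in severity during the course of the study". The anchor is the study, not the first carnitine dose.
- **Reporting period (9.2.3.1).** AEs are reportable over "the period from the initiation of any study procedures to the end of the study treatment follow-up", and "the study treatment follow-up is defined as 14 days following the last administration of study treatment".
- **Timing (4.2, 4.2.4, Table 1).** Visit 1 is day 0. Carnitine dosing is listed at Visit 2 (nominal day 84), and Visit 4 is nominal day 99.
- **Severity (9.2.2.1).** "If the intensity of an AE worsens during study drug administration, only the worst intensity should be reported on the AE page". The next sentence reads: "If the AE lessens in intensity, no change in the severity is required".
- **Upkeep of the entry (9.2.2.3).** For each AE, "an AE entry on the appropriate form will be completed using the above classifications as soon as possible, updating as necessary". No section asks for a second entry, a grade at first dose or a date of worsening.
- **Analysis (5.1, 6.2, 6.6).** Tolerability is a secondary endpoint. It is reported as the proportion of subjects with the event and its 95% confidence interval, and toxicities are summarised by incidence and grade. Neither 6.2 nor 6.6 limits the count to time on supplement.
- **Table 1.** The adverse-event row is marked only from Visit 2 onward, which does not match 9.2.3.1.

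**The concern.** This is a single-arm study in which every patient has a long supplement-free lead-in and then about two weeks of carnitine. With no control group, timing relative to the first dose is a main source of evidence for separating a carnitine effect from background.

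The effects expected in section 7.3 are non-specific gastrointestinal complaints: "these include transient nausea and vomiting, abdominal cramps, and diarrhea". Such complaints can already be present before dosing. If one is open at Visit 2 and gets worse on carnitine, the entry the protocol describes carries one grade and nothing that places the worsening after the first dose. At stake is whether the reported proportion describes carnitine, or carnitine plus 12 weeks of background.

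**Working it through.** **Design figure.** The plan gives no numerical target for tolerability. Its one design figure is 80% power for the primary endpoint with n = 10. A paired t-test with change 8.5, SD of differences 8.6 and two-sided 5% gives 79.4%, so that figure reproduces. Only n = 10 carries over to this point.

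**Step 1: share of time before carnitine.** From Table 1, 84 of the 99 nominal days to Visit 4 precede dosing: 84/99 = 85%. This shows that lead-in events have ample time to arise. It is not the probability that an AE is open at Visit 2.

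**Step 2: what the recording rule does.** Take three hypothetical patients, each with one AE entry:

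| Patient | Week 6 | Visit 2, before dosing | On carnitine | Grade on the entry | Worsened on carnitine? |
|---|---|---|---|---|---|
| A | 1 | 1 | 2 | 2 (worst grade kept) | Yes |
| B | 2 | 1 | 1 | 2 (no downgrade required) | No |
| C | 2 | 1 | 2 | 2 (no change needed) | Yes |

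All three end as one grade 2 entry, and section 6.2 counts all three. The entry as described does not separate A and C from B.

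**Step 3: effect on the proportion (counts assumed).** Of 10 patients, 3 have an AE open at Visit 2, w of those 3 worsen on carnitine, and 1 other patient has a new event after first dose.

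- Count under 6.2, with no window: (3 + 1)/10 = 4/10, whatever w is. Exact (Clopper-Pearson) 95% CI 12.2–73.8%.
- Count of onset or worsening after first dose: (w + 1)/10.

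| w | Onset or worsening after first dose | Exact 95% CI | Excess under 6.2 |
|---|---|---|---|
| 0 | 1/10 | 0.3–44.5% | 30 points |
| 1 | 2/10 | 2.5–55.6% | 20 points |
| 2 | 3/10 | 6.7–65.2% | 10 points |
| 3 | 4/10 | 12.2–73.8% | 0 points |

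Each reclassified subject moves the proportion by 1/10 = 10 points. Patients whose AEs resolved before Visit 2 would also be counted under 6.2. The illustration assumes there are none.

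**Step 4: does either half of the fix work alone?** Splitting the record while leaving 6.2 unchanged still gives 4/10, because 6.2 counts subjects with any event. Changing 6.2 alone does not suffice either: worsening after first dose cannot be derived from an entry that holds only the worst grade. Both must change.

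**The case against.** A reader might infer that on-supplement worsening is lost from the tolerability result. The documents do not support that. In the simple grade 1 to grade 2 case, 9.2.2.1 keeps the on-carnitine grade, 6.6 summarises grade, and 6.2 counts the subject. The worsening would drop out only if an analyst counted by onset date (1/10 in the w = 2 case above), and the plan specifies no such count. As written, the error tends toward over-attribution.

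The plan also holds other information: five-level relatedness (9.2.2.3), symptom assessments at all four visits, a Week 13 call recording symptoms and side effects (4.2.6), and a record of episodes when the supplement is withheld (6.3). These may allow partial reconstruction. However, relatedness attaches to the entry, not to a change within it, and no section says that the symptom assessments are graded or feed the tolerability count.

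Two further limits stand. The case report form is not among the documents, so it may date grade changes; the point concerns the entry as the protocol describes it. And if the AE row of Table 1 governs, a week 6 complaint may have no entry before Visit 2, which would shrink the lead-in contribution. Against that, 9.2.3.1 and the AE questioning at every contact in 8.2 point the other way, and a complaint recorded at Visit 2 before dosing meets the same difficulty.

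**Conclusion.** The point holds as a gap in attribution. Under the stated recording rule and the count without a window, the carnitine tolerability proportion combines background and on-supplement events, and worsening of an AE open at first dose cannot be identified from its entry. The worst-intensity sentence contributes, but the missing on-supplement definition in 6.2 and 6.6 matters as much.

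The size is 10 percentage points per reclassified subject. In the illustration the excess runs from 0 to 30 points, and is 10 points (4/10 against 3/10) when 2 of 3 open AEs worsen. The counts are assumed, since the documents give no background rate of gastrointestinal complaints. With n = 10 the confidence intervals are wide in any case. The conclusion assumes that the reporting period in 9.2.3.1 applies and that the form holds no dated grades beyond what the protocol describes. It affects a descriptive secondary endpoint; the plasma carnitine primary endpoint is untouched.

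**What to change.** 1. **Section 9.2.2.1.** When an AE or symptom present before the first carnitine dose increases in grade after it, enter it as a new AE with its own onset date, grade and relatedness. Keep the worst-grade rule only for AEs that begin after the first dose.
2. **Visit 2.** Record the grade of any open AE or symptom before dosing.
3. **Sections 6.2 and 6.6.** Compute the carnitine tolerability proportion from AEs with onset or worsening after the first dose. Report lead-in AEs separately.
4. **Table 1 and 9.2.3.1.** Reconcile the AE row, which starts at Visit 2, with the reporting period, which starts at the first study procedure.

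The cost is a few extra AE entries and one form instruction in a 10-patient study, plus short edits to the text. Pre-dose grades and worsening dates are best captured prospectively, so the change should be in place before patients reach Visit 2.

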9.2.2.3 Relatedness

1) Definite: the AE is clearly related to the research procedures

2) Probably: the AE is likely related to the research procedures

3) Possible: the AE may be related to the research procedures

- 4) Unlikely: the AE is doubtfully related to the research procedures
- 5) Unrelated: the AE is clearly not related to the research procedures

Possibly related to participation in the research: There is a reasonable possibility that the adverse event experience, or outcome may have been caused by the procedures involved in the research.

For each identified AE, an AE entry on the appropriate form will be completed using the above classifications as soon as possible, updating as necessary. Reporting procedures should be started immediately (within 24 hours) upon learning of a SAE or UP.

9.2.3 Interpretation of Definitions

9.2.3.1 AE and UP Reporting Period

The study period during which AEs must be reported is normally defined as the period from the initiation of any study procedures to the end of the study treatment follow-up. For this study, the study treatment follow-up is defined as 14 days following the last administration of study treatment.

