2.1 Objectives

This is a single-center, prospective study enrolling 10 PAH patients. All eligible participants will be given carnitine supplements for 2 weeks.

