3.3 Supplement Dosing

A 14-19-day supply of Carnitine supplements will be provided to the subject at Visit 2. The VUMC Pharmacy for Research will supply Nature's Bounty L-Carnitine 500mg caplets to be taken by mouth. For subjects weighing <90kg, I- carnitine will be taken at 1.5g twice a day. For subjects weighing >90kg, I-carnitine will be taken at 50 mg/kg/day split between 2 doses. Dosing for these participants will be rounded to the next whole pill to achieve approximately 50 mg/kg per day. Dosing will be incrementally titrated by 25- 50% in the event of intolerance and/or side effects limiting subject's compliance to prescribed regimen.

4 Data Collection

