4.2.6 Telephone Contact (Week 13)

The research coordinator will call the subject a week after beginning the carnitine supplement to review and record symptoms, potential side effects, and changes in medications. Study compliance will also be assessed and reinforced.

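### AE reporting runs to 14 days after the last dose, but no contact is scheduled after Visit 4, so events late in that period may be under-ascertained

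*Combined protocol and SAP*

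**What the plan says.** Section 9.2.3.1 defines the AE reporting period as "the period from the initiation of any study procedures to the end of the study treatment follow-up", and then fixes its end for this trial: "the study treatment follow-up is defined as 14 days following the last administration of study treatment".

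The contact schedule is in section 4.2 and Table 1. Section 4.2 opens with "This study will consist of four visits", the last at Week 14. There are three telephone contacts: before Visit 1, at Week 11 and at Week 13. The last column of Table 1 is Visit 4, Day 99 ± 5.

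On supplementation, section 2.1 says "All eligible participants will be given carnitine supplements for 2 weeks". Section 3.3 adds "A 14-19-day supply of Carnitine supplements will be provided to the subject at Visit 2". Section 4.2.5 hands out a two-week supply at Visit 3, the next day. Dosing therefore starts on Day 84 or 85, and Visit 4 falls at about its end.

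On how AEs are found, section 8.2 says "Surveillance for AEs will consist of questioning subjects about potential AEs at every study contact". It adds two other routes: subjects reporting events themselves, and vital signs and examinations at visits. The only AE-directed call during supplementation is the one in section 4.2.6: "The research coordinator will call the subject a week after beginning the carnitine supplement to review and record symptoms, potential side effects".

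**The concern.** The protocol sets a post-dose reporting period specific to this trial but schedules nothing at its end to collect what happened in it. Of the three routes in section 8.2, two need a contact or a visit. After Visit 4 only the third, self-report, remains. Ascertainment therefore changes part-way through one stated period, from questioning to volunteering.

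It also differs between subjects. Sections 6.3 and 9.2.4 keep subjects who stop the supplement early on the visit schedule, so Visit 4 can fall well inside their 14 days. A subject who completes dosing has Visit 4 at the very start of theirs.

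At stake is the tolerability endpoint in section 5.1 (side effects, AEs and SAEs). Section 6.2 analyses it as the proportion of subjects with an event and a 95% confidence interval. The opening rationale presents this pilot as preparation for a later mechanistic study, so its tolerability figures are likely to be carried forward.

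**Working it through.** The plan gives no figure of its own here, so the check is day arithmetic on its schedule.

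**Inputs**
- Supplement start: Day 84 (Visit 2) or Day 85 (Visit 3), from Table 1 and sections 3.3, 4.2.4 and 4.2.5.
- Last dose on the nominal two-week course: Day 98 or 99.
- Visit 4: Day 99, window Day 94 to 104 (Table 1).
- Supply: 14 to 19 days (section 3.3).
- End of AE reporting: last dose + 14 days (section 9.2.3.1).

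**Formulas**
- Days after the last scheduled contact = (last dose + 14) − Visit 4 day.
- On- and post-supplement window = (last dose + 14) − start day.
- Full reporting period = (last dose + 14) − Day 0. The start is defined by the first study procedure and is taken here as Visit 1.

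**Nominal schedule, Visit 4 on Day 99**

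| Start | Last dose | Reporting ends | Days after Visit 4 | Share of on- and post-supplement window | Share of full period |
|---|---|---|---|---|---|
| 84 | 98 | 112 | 13 | 13/28 = 46% | 13/112 = 12% |
| 84 | 99 | 113 | 14 | 14/29 = 48% | 14/113 = 12% |
| 85 | 98 | 112 | 13 | 13/27 = 48% | 13/112 = 12% |
| 85 | 99 | 113 | 14 | 14/28 = 50% | 14/113 = 12% |

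**Range over the Visit 4 window and supply, with Visit 2 held at Day 84**
- Lowest: 14-day supply from Day 84, last dose Day 97, Visit 4 on Day 104. Reporting ends Day 111, and (111 − 104)/(111 − 84) = 7/27 = 26%.
- Highest: start Day 85, Visit 4 on Day 94, dosing to that day. Reporting ends Day 108, and (108 − 94)/(108 − 85) = 14/23 = 61%.

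Visit 2 has its own ± 5-day window. Moving it as well widens the extremes, but some of those combinations leave far less than two weeks of dosing, so I do not rely on them.

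**Early stopper**
- Start Day 85, stop after 7 days (last dose Day 91), Visit 4 on Day 99. Reporting ends Day 105, and (105 − 99)/(105 − 85) = 6/20 = 30%.

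**Effect on the tolerability proportion**
- One subject among 10 is 1/10 = 10 percentage points.
- Section 6.2 does not name an interval method. Assuming the exact binomial interval, 0/10 gives 0–31% and 1/10 gives 0.3–45%.

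**With a contact at last dose + 14 (nominally Day 112 or 113)**
- Days after the last scheduled contact fall from 13–14 to 0.

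**The case against.** The strongest reply is that a reporting period is not a contact schedule. Section 9.2.3.1 says how long AEs must be reported; it does not promise questioning throughout. Self-report is a planned route in section 8.2, and section 9.2.3.2 requires any AE to be passed on within 24 hours. This stands in part: the days after Visit 4 are not unmonitored. A reader might infer that late events would be missed, and the documents do not support that. But the 24-hour rule operates only once the team learns of an event, and no section schedules a contact through which it would ask.

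A second reply concerns size. A reader might infer that half the safety window is never actively assessed. That holds only for the nominal 27- to 29-day window, which the protocol does not itself define. Over the period it does define, the share is about 12%. A reader might also infer that no contact at all follows the last dose. That can be false: dosing may end on Day 97 or 98, and Visit 4 then includes a symptom assessment, an examination and an AE entry after the last dose. The accurate statement is that nothing is scheduled after Visit 4.

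Third, the effects listed in section 7.3 are mainly mild gastrointestinal symptoms and an odor while taking the supplement. Visit 3, the Week 13 call and Visit 4 are well placed to pick these up. This stands, and it limits how many events are likely to be lost. The documents give no rate of delayed events, so no amount of bias can be stated. A subject already counted during dosing would not change the proportion either.

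**Conclusion.** The mismatch is real, and no other section cures it. The only later contact mentioned, in section 9.5, depends on future investigations and is not an AE contact. For a nominal completer, the last 13–14 days of the stated reporting period rest on self-report alone, in the proportions worked out above.

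The consequence is possible under-ascertainment in a secondary endpoint, not a demonstrated undercount. The 10-point figure assumes that the missed event is that subject's only one, and that the proportion in section 6.2 is meant to cover the whole period in section 9.2.3.1, which section 6.2 does not say. Plasma carnitine, the primary endpoint, is untouched. The change is still worth making, because the period is the protocol's own and the remedy is small.

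**What to change.** Reconcile section 4.2 and Table 1 with section 9.2.3.1 by adding one telephone contact at the end of the 14-day follow-up, using the same symptom and side-effect questions as the Week 13 call. Date it from each subject's recorded last dose, nominally Day 112 or 113. A subject who stopped early enough that the 14 days end by Visit 4 would not need it.

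The cost is at most 10 calls and one Table 1 column, with no new procedure. Ending the reporting period at Visit 4 would also make the sections agree, but only by shortening a safety period the protocol has already set, so I do not suggest it.
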